6.11 Concomitant Medication Assessments

A concomitant medication is any medication that the subject has been taking prior to enrollment and that the subject is expected to continue to take for some portion of the trial, as well as any medication other than the investigational product that the subject takes during the course of the trial.

The medications or treatment for controlling hypoglycemia must be recorded as concomitant medications in the CRF. Any medication given to treat hyperglycemia is considered a rescue therapy and should be recorded in the concomitant medication log.

Changes from baseline anti-hypertensive therapy and their rationale must be recorded in the CRF.

All prescription and over-the-counter medications, including vitamins and herbal supplements, that subjects receive during the trial must be documented on the CRF. This documentation should continue until the subjects complete the study.

Concomitant medications will be coded using the World Health Organization Drug Dictionary (WHO-DD). A table of concomitant medications based on the anatomic

therapeutic chemical classification (ATC) and preferred name will be produced. A listing of concomitant medications will include all medications taken by any subjects during the course of the study.

6.12 Removal of Patients from the Trial or Discontinuation of Investigational Product Administration

The investigator must emphasize to potential subjects the importance of continued participation for the full duration of the trial during the informed consent process. Potential subjects should be informed that the trial procedures will allow additional medications to control hyperglycemia or other adverse conditions. It is also important to emphasize that missing data and missed visits could affect the entire trial. If subjects are dissatisfied with the conduct of the trial but have not withdrawn, the investigator should make an effort to address their concerns and retain them in the trial if possible. In doing so, investigators must be careful that the efforts do not cross over into coercion. Investigator should encourage a subject to remain in the study even if the investigational product administration is stopped so that safety information can be collected.

Participation in a clinical trial is voluntary. A subject can withdraw from the study at any time. The sponsor or investigator may terminate the study for medical or administrative reasons. If a decision is made to withdraw a subject from the study, no further investigational product should be administered. Even if the subject discontinues study medication, every attempt should be made to complete all required study evaluations and procedures. Reasons for all withdrawals should be recorded on the CRF. Examples of reasons for withdrawal include:

1. A protocol violation has occurred,
2. A serious or intolerable adverse event has occurred,
3. A clinically significant change in a laboratory parameter has occurred,
4. The sponsor or investigator terminates the study, or
5. The patient requests to be withdrawn from the study.

Subjects who do not complete the study but who have received investigational product should have a follow-up examination, including a physical examination, vital signs, ECG and clinical laboratory tests according to [Section 7](#).

Subjects who withdraw from the study will not be replaced.

6.13 Appropriateness of Measurements

The percentage of HbA1c is a widely used measure of chronic glycemia, reflecting average blood glucose levels over a 2- to 3-month period of time. It is an accepted surrogate marker for risk of microvascular complications and is widely used as a measurement for the adequacy of glycemic management. Other study procedures and measurements in this protocol are widely used and generally recognized as reliable, accurate, and relevant for subjects with T2DM.

7 STUDY ACTIVITIES

The study activities at each clinic visit listed below are presented in [Appendix 1](#). The required laboratory tests scheduled at each visit are listed in [Appendix 2](#). Detailed study procedures are described in [Section 6](#).

A visit window of ± 3 days is allowed for all visits except visit V1. Visit V1 is to be scheduled 3 days after visit S5 is complete and can be extended to 5 days depending on HbA1c value availability.

7.1 Screening (Up to 15 weeks prior to randomization, visit S1)

The screening can be performed from 3 weeks to 3 days before the start of the washout period for subjects who are taking background OHA or 3 weeks to 3 days before the start of the run-in period for subjects who are treatment naïve. At the screening visit the study investigator will:

- Explain the content of informed consent to the subject and collect signed informed consent
- Obtain medical history and demographic information
- Perform a complete physical examination including height and weight
- Measure vital signs, including blood pressures, pulse, temperature, and respiratory rate
- Perform a 12-lead ECG measurement
- Draw blood if a minimum 10-h fast has been completed by the subject as described in [Section 6.7.2.1](#). The specific laboratory tests scheduled for this visit are listed in [Appendix 2](#)
- Collect a clean-catch, mid-stream urine sample for drug abuse screening, urinalysis, and for UPT for all females
- Evaluate the subject's suitability for enrollment according to the inclusion and exclusion criteria based on the information collected.

7.2 Washout and Run-in Periods (Up to 12 weeks prior to randomization)

The washout and run-in period is required for all enrolled subjects who are taking an OHA. Enrolled treatment naïve subjects will not require any washout and will enter the run-in period.

7.2.1 Washout of OHA (Visits S2 and S3)

Two visits will be conducted during the washout period. Visit S2 is a clinic visit. At Visit S3 each subject will be evaluated by the investigator or study staff via a phone interview 2 weeks after washout starts; there will be no on-site evaluation at Visit S3.

7.2.1.1 Visit S2 (subjects taking one OHA)

At the S2 visit the study investigator will:

- Evaluate inclusion/exclusion criteria for eligibility
- Counsel subject on appropriate diet and exercise
- Dispense glucometer and train subject in SMBG determination and recording
- Discontinue the OHA for 10 weeks if a subject is taking a TZD; discontinue the OHA for 6 weeks if a subject is taking a non-TZD OHA
- Collect clean-catch, mid-stream urine for urinalysis and UPT for women of child bearing potential.
- Assess pre-treatment signs and symptoms and record pre-treatment concomitant medications.

7.2.1.2 Visit S3 – Phone interview (subjects in washout)

At the S3 visit the study investigator will:

- Review daily SMBG and glycemic control record for each day during the prior 2 weeks
- Assess any signs and symptoms of severe hyperglycemia, including increased urination, increased thirst, weight loss, and changes in vision
- Assess pre-treatment signs and symptoms and record pre-treatment concomitant medications.

7.2.2 Run-in Period:

7.2.2.1 Visit S4 (Week -2)

At the S4 visit the study investigator will:

- Counsel subject on appropriate diet and exercise (for subjects who are treatment naïve and do not require washout)
- Dispense glucometer and instruct subject in SMBG determination and recording (for subjects who are treatment naïve and do not require washout)
- Review glycemic control diary and SMBG (for subjects who complete 6 or 10 weeks of washout)
- Measure vital signs, including blood pressures, pulse, temperature, and respiratory rate
- Collect clean-catch, mid-stream urine sample for urinalysis and UPT for women of child bearing potential.
- Dispense run-in kit for run-in period
- Assess pre-treatment signs and symptoms and record pre-treatment concomitant medications.

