9.2 Determination of Sample Size

Approximately 320 subjects will be randomized and equally allocated to receive bexagliflozin tablets, 5 mg, 10 mg, 20 mg, or placebo.

The sample size calculation for this study is based on a two group t-test with a two-sided significance at the 5% level and the following assumptions:

- 1) The placebo-corrected population mean change from baseline to Week 12 in HbA1c in the highest dose group of 20 mg will be -0.5%.
- 2) The pooled standard deviation for the change from baseline to Week 12 in HbA1c for the active and placebo groups will be 0.9%.

Under the above assumptions, an estimated sample size of 70 evaluable subjects per treatment arm yields approximately 90% power to detect a treatment difference between bexagliflozin and placebo. A sample size of 80 per arm has been selected to account for a potential drop-out and to allow adequate safety evaluation. The total sample size for this study will be 320 subjects.

This study will be conducted at multiple investigative sites and will likely involve variable numbers of subjects at each site. Enrollment will be on a competitive basis but will be capped at 32 subjects from each site.

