2.2.3 Efficacy Assessments

Efficacy assessments will include blood draws for a glycemic control laboratory panel, including HbA1c and FPG, body weight, and systolic and diastolic blood pressure (BP).

Blood samples for HbA1c and FPG will be obtained at Screening (Visit S1), Run-in (Visit S5), Treatment Period Visits 2, 3, 4 and Follow-up Visit 5. Body weight will be measured at Screening (Visit S1), Washout (Visit S2), Run-in (Visit S5), Treatment Period Visits 2, 3, 4 and Follow-up Visit 5. Supine, sitting and standing

BP measurements will be obtained at Screening (Visit S1), Run-in (Visits S4 and S5), Treatment Period Visits 2, 3, 4 and Follow-up Visit 5.

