3.1.5 Baseline and Change from Baseline

Baseline is defined as the last non-missing value obtained immediately prior to administration of the first dose. For each post-baseline value, change from baseline will be calculated by subtracting the baseline assessment value from the post-baseline assessment for each subject (i.e., post-baseline assessment – baseline assessment).

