3.8.2 Secondary Efficacy Endpoints

The secondary efficacy endpoints, fasting plasma glucose, sitting systolic and diastolic blood pressure and weight, will be analyzed using the same MMRM ANCOVA model used for the primary efficacy analysis on the full analysis set. In addition, for each secondary efficacy endpoint, the least squares means and standard errors of the change from baseline over time by treatment group will be presented graphically. Sensitivity analyses will not be performed on the secondary efficacy endpoints.

For each subject, post-baseline HbA1c values will be reviewed and subjects with at least one post-baseline HbA1c value $<7\%$ will be flagged. HbA1c values obtained after start of rescue medication will be excluded from this analysis. The number and percentage of subjects with at least one HbA1c value $<7\%$ will be summarized by treatment group for the full analysis set. A logistic model will be used to characterize treatment differences in the proportions of subjects with at least one post-baseline HbA1c value $<7\%$. For this model, the dependent variable will take values of $1 = '<7\%'$ or $0 = '≥7\%'$ and the predictor variables will include treatment, study center, baseline HbA1c and prior anti-diabetic treatment status. Odds ratio for the treatment difference versus placebo, its 95% confidence interval and the associated p-value will be presented.

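### The S4 run-in blood pressure normally enters no systolic or diastolic model; adding it as a second baseline covariate may sharpen two exploratory endpoints at almost no cost

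*Protocol*

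**What the plan says.** **Collection.** Protocol 7.2.2.1 (visit S4, Week -2) instructs the investigator to "Measure vital signs, including blood pressures, pulse, temperature, and respiratory rate", and Protocol 7.2.2.2 repeats this at S5. SAP 2.2.3 lists all the visits before randomization: "BP measurements will be obtained at Screening (Visit S1), Run-in (Visits S4 and S5". Protocol 7.3.1 and the Schedule of Events show no vital signs at V1, the day of randomization.

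**Baseline.** One rule in SAP 3.1.5 covers every variable: "Baseline is defined as the last non-missing value obtained immediately prior to administration of the first dose". For blood pressure this normally means S5. S4 becomes the baseline only if S5 is missing.

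**Model.** Under SAP 3.8.2, "sitting systolic and diastolic blood pressure and weight, will be analyzed using the same MMRM ANCOVA model used for the primary efficacy analysis". That model (SAP 3.8.1) has one baseline covariate with one slope shared by all visits.

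**Status.** Blood pressure over time is a named secondary objective (Protocol 2.2, SAP 2.1). Both documents treat all secondary endpoints as exploratory, with no multiplicity adjustment (Protocol 9.1.2, SAP 3.1.4).

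**Context.** The blood pressure exclusion in Protocol 4.3 applies at screening (S1), before any washout of the oral agent. Protocol 5.6 lets investigators alter blood pressure drugs during run-in, but during treatment only when medically necessary.

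**The concern.** Blood pressure varies from visit to visit, so a baseline from one visit measures a subject's usual level imperfectly. S4 is a second measurement of that level, already planned for every subject. It has neither of the drawbacks of S1: it comes after any washout, and it is not the visit at which the cut-off is applied.

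Because S4 precedes randomization, adjusting for it does not bias the comparison between arms. If S4 carries information about later blood pressure beyond what S5 carries, leaving it out makes the dose-versus-placebo intervals for systolic and diastolic pressure wider than they need be. What is at stake is the precision of those two secondary analyses.

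**Working it through.** **Inputs from the documents**
- Sample size basis (Protocol 9.2): "two group t-test with a two-sided significance at the 5% level"; the placebo-corrected HbA1c change "in the highest dose group of 20 mg will be -0.5" (percentage points); the SD of change "for the active and placebo groups will be 0.9" (percentage points); "70 evaluable subjects per treatment arm yields approximately 90% power"; 80 randomized per arm.
- For blood pressure: no SD, correlation, power or precision figure. All correlations below are assumptions.

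**Step 1: the plan's own figure.** By the normal formula, n = 2 × (1.960 + 1.282)² × 0.9² / 0.5² = 68.1, so 69 per arm. At 70 per arm the power is 90.8% (normal) or 90.4% (noncentral t). The stated 70 and 90% reproduce. They concern HbA1c only and are unaffected by this point.

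**Step 2: formula for blood pressure.** At a single visit, analysing change from S5 with S5 as covariate gives the same treatment contrast as analysing the Week 12 value with S5 as covariate. Let r5 = corr(S5, Week 12), r4 = corr(S4, Week 12) and r45 = corr(S4, S5).
- Residual variance, S5 only: V1 = 1 − r5².
- Residual variance, S5 and S4 as separate covariates: V2 = 1 − (r5² + r4² − 2·r45·r5·r4) / (1 − r45²).
- Proportional cut: 1 − V2/V1 = (r4 − r5·r45)² / [(1 − r45²)(1 − r5²)].
- Equivalent size of an arm of 80: 80 × V1/V2.

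Example with all correlations 0.6: V1 = 1 − 0.36 = 0.640. V2 = 1 − (0.36 + 0.36 − 0.432)/0.64 = 0.550. The cut is 0.0576/0.4096 = 14%, and 80 × 0.640/0.550 = 93.

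**Step 3: range of assumptions**

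| Assumption | r45 | r5 | r4 | V1 | V2 | Cut | 80 acts like |
|---|---|---|---|---|---|---|---|
| Equal correlations | 0.50 | 0.50 | 0.50 | 0.750 | 0.667 | 11% | 90 |
| Equal correlations | 0.60 | 0.60 | 0.60 | 0.640 | 0.550 | 14% | 93 |
| Equal correlations | 0.70 | 0.70 | 0.70 | 0.510 | 0.424 | 17% | 96 |
| S4 and S5 closer to each other | 0.65 | 0.55 | 0.52 | 0.698 | 0.652 | 7% | 86 |
| S4 and S5 closer to each other | 0.75 | 0.60 | 0.57 | 0.640 | 0.607 | 5% | 84 |
| S4 less predictive | 0.60 | 0.60 | 0.50 | 0.640 | 0.609 | 4.8% | 84 |
| S4 less predictive | 0.60 | 0.60 | 0.40 | 0.640 | 0.638 | 0.4% | 80 |
| Serial decay (r4 = r5 × r45) | 0.60 | 0.60 | 0.36 | 0.640 | 0.640 | 0% | 80 |

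The equal-correlation cuts correspond to standard errors lower by 5.7%, 7.3% and 8.9%. The 5–7% cuts correspond to 2.6–3.3%. With equal correlations the mean of S4 and S5 is the optimal combination, so a simulation using that mean also checks the formula: at r = 0.6 and 80 per arm it gave an 8.2% lower standard error, against 7.3% from the formula.

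**Step 4: two covariates versus averaging.** Using the mean of S4 and S5 as the only covariate gives 1 − (r4 + r5)² / [2(1 + r45)]. With r5 = r45 = 0.6, the standard error relative to S5 alone changes as follows:
- r4 = 0.50: −1.4% with the mean, −2.4% with two covariates.
- r4 = 0.40: +3.6% with the mean, −0.2% with two covariates.

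Averaging starts to lose once r4 falls below 0.6 × (√3.2 − 1) = 0.47. With separate covariates the S4 weight is estimated and can go to zero.

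**Step 5: scale and cost.** Assume a systolic SD of 12 mmHg, r5 = 0.6 and 80 per arm. The 95% half-width with S5 alone is 1.96 × 12 × √0.640 × √(2/80) = 2.98 mmHg. With S4 added it is 2.76 under equal correlations, or 2.98 × (1 − 0.026) = 2.90 in the 5% case. One degree of freedom among about 320 subjects costs roughly 1/320 = 0.3% of variance.

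**The case against.** The strongest reply is that the plan contains no mistake here. Taking the last value before dosing is conventional, pre-specified, and applied to every variable, and SAP 3.8.2 uses one common model for glucose, blood pressure and weight. Dose selection rests on HbA1c, and no blood pressure success criterion exists. All of this stands.

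The design also gives reasons to expect S4 to predict less well than S5. Drug changes permitted in run-in fall mainly between the two visits, so S4 may reflect a superseded regimen. Treatment-naïve subjects first receive diet and exercise counselling at S4 (Protocol 7.2.2.1). S4 is also further from Week 12. These points stand too, and are why the range must reach down to zero.

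The warning that S4 could reduce precision is sound for averaging (Step 4). It does not apply to a separately estimated S4 slope, apart from the one degree of freedom.

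Some stronger readings are tempting but unsupported:
- *The S5-only analysis is biased or wrong.* It is not; randomization protects the comparison with either baseline.
- *Precision is gained for every dose at every visit at no cost.* Only Week 12 was calculated, with weights optimal for that visit. The SAP model shares one baseline slope across visits, so the result does not carry over directly to Weeks 2 and 6, and the gain may be nil.
- *The eligibility rule, which averages two sitting measurements, shows that a single baseline reading is too noisy.* That rule concerns measurements at screening and says nothing about averaging across visits. Protocol 6.4.1 does not state how many sitting readings make up a visit's value, so it is not established that the S5 baseline is one reading.

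**Conclusion.** The point holds as a low-priority efficiency suggestion. The S4 sitting pressure is collected before randomization and, unless S5 is missing, enters neither blood pressure model. Used as a second covariate, it would reduce Week 12 residual variance by between about 0% and 17%, depending on correlations that the documents do not give. The 11–17% end requires S4 to predict Week 12 as well as S5 does. The 5–7% figures assume that S4 and S5 correlate more with each other (0.65–0.75) than with Week 12 (0.52–0.60). Zero is reached under serial decay, and drug changes in run-in could have a similar effect.

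The primary HbA1c analysis, the sample size and the type I error are untouched. The endpoints concerned are exploratory.

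**What to change.** In SAP 3.8.2, before unblinding, specify that the systolic and diastolic MMRMs include the S4 sitting value as a second baseline covariate beside the S5 baseline. Where S4 is missing, substitute the S5 value so that no subject is dropped. Where S5 is missing, SAP 3.1.5 already makes S4 the baseline, and both terms then take that value. Do not average the two readings. Leave SAP 3.1.5 unchanged, so that S5 remains the baseline for change scores and descriptive tables.

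The cost is one SAP sentence and one model term (one degree of freedom) per endpoint, with no extra visit or measurement. It should be settled in advance, because a covariate added after unblinding would look chosen from the data.

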7.2.2.2 Visit S5 (Days -3 to -5)

At the S5 visit the study investigator will:

- Confirm inclusion/exclusion criteria for eligibility and review run-in drug compliance
- Perform an abbreviated physical examination including weight
- Review glycemetic control diary and SMBG results
- Measure vital signs, including blood pressures, pulse, temperature, and respiratory rate
- Perform a 12-lead ECG measurement
- Draw blood from subject if a fast of 10 h or greater has been completed as described in [Section 6.7.2.1](#). The specific laboratory tests scheduled for this visit are listed in [Appendix 2](#)
- Collect clean-catch, mid-stream urine sample for urinalysis and UPT for women of child bearing potential.
- Assess pre-treatment signs and symptoms and record pre-treatment concomitant medications.

7.3 Treatment Period (week 1 to week 12)

At the end of the run-in period, subjects who have successfully completed run-in period and continue to meet inclusion/exclusion criteria will be randomized and enter the treatment period.

7.3.1 Visit V1 (Day 1 of week 1)

Visit 1, day of randomization, must be conducted after the HbA1c value from the sample of S5 visit is available for eligibility confirmation.

At the V1 visit the study investigator will:

- Confirm HbA1c value of 7.0 to 8.5% based on the S5 sample results
- Review SMBG and glycemetic control record
- Dispense investigational product based on randomization
- Assess adverse events and record concomitant medications

7.3.2 Visit V2 (week 2)

At the V2 visit the study investigator will:

- Review SMBG and glycemetic control record
- Measure vital signs, including blood pressures, pulse, temperature, and respiratory rate
- Draw blood from subjects who have fasted a minimum of 10 h as described in [Section 6.7.2.1](#). The specific laboratory tests scheduled for this visit are listed in [Appendix 2](#)

- Collect blood specimens for sparse PK sampling from selected subjects in participating centers
- Collect clean-catch, mid-stream urine sample for urinalysis in all subjects and for UPT for women of child bearing potential
- Assess adverse events and record concomitant medications

7.3.3 Visit V3 (week 6)

At the V3 visit the study investigator will:

- Review SMBG and glycemic control record
- Measure vital signs, including blood pressures, pulse, temperature, and respiratory rate
- Draw blood from subjects who have fasted a minimum of 10 h as described in [Section 6.7.2.1](#). The specific laboratory tests scheduled for this visit are listed in [Appendix 2](#)
- Collect blood specimens for sparse PK sampling from selected subjects in participating centers
- Collect clean-catch, mid-stream urine sample for urinalysis in all subjects and for UPT for women of child bearing potential
- Assess adverse events and record concomitant medications.

7.3.4 Visit V4 (week 12)

At the V4 visit the study investigator will:

- Review SMBG and glycemic control record
- Perform an abbreviated physical examination including weight
- Measure vital signs, including blood pressures, pulse, temperature, and respiratory rate
- Perform a 12-lead ECG measurement
- Draw blood from subjects who have fasted a minimum of 10 h as described in [Section 6.7.2.1](#). The specific laboratory tests scheduled for this visit are listed in [Appendix 2](#)
- Collect blood specimens for sparse PK sampling from selected subjects in participating centers
- Collect clean-catch, mid-stream urine sample for urinalysis in all subjects and for UPT for women of child bearing potential
- Retrieve remaining study medication and record the number of remaining tablets
- Assess adverse events and record concomitant medications.

